11.1.1. Handling Missing Data

For ITT population, the analyses with imputation for missing data will be performed for the primary efficacy endpoint (pain score change from baseline to 6 months). For subjects without the primary efficacy endpoint, the following imputation methods will be considered:

- For subjects with an early drop-out reason not related to death or AEs, the last available value (LOCF) of the subject will be used for the missing 6-month value. For early discontinued subjects due to AEs, the maximum value of all available 6-month pain score will be imputed for the missing 6-month value. For early discontinued subjects due to death, no imputation will be performed and therefore will not be included in the 6-month analyses if they are discontinued prior to the 6-month visit.

No imputation for missing values will be performed for other variables.

11.2. Outcome of at least 50% Reduction in Average Pain Score from Baseline to 6-Month

The percent reduction in the average pain score (determined by the 7-Day Daily Pain and Sleep Interference Diary) from baseline to 6-month follow-up will be calculated for each subject as follows:

$$\% \text{ reduction} = (\text{Baseline Pain Score} - \text{6-month Pain Score}) \div \text{Baseline Pain Score} \times 100\%.$$

The percentage of subjects with at least 50% reduction in pain from baseline to the 6-month follow-up and the corresponding 95% confidence intervals based on the binomial distribution will be calculated for each study group. Fisher's exact test will be used to compare the percentage of subjects with at least 50% reduction in pain among the three study groups. The comparison between the placebo group and each of the two VM202 group will also be performed by Fisher's exact test. The 95% confidence interval of the difference between placebo and each of the two VM202 group in the percentage of subjects with at least 50% reduction will be derived by the two-sample normal distribution.

The percentage of subjects with at least 20%, 30%, 40%, 60%, 70%, and 80% reduction in pain and the corresponding 95% confidence intervals based on the binomial distribution will also be provided.

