4. SAMPLE SIZE JUSTIFICATION

The sample size for this Phase 2 study was chosen to estimate effect sizes and variability for a pivotal study. Based on the 12 subjects in the Phase I study (Protocol VMDN-001), the overall mean VAS reduction from baseline to 6 months is about 23 mm with a standard deviation of about 25 mm.

This Phase II study has two VM202 dose groups (16 mg and 32 mg) and a placebo group. The study goal is to identify any difference in mean reduction in pain as measured by the Daily Pain and Sleep Interference Diary between each of the two VM202 groups against the placebo group. Based on the two-sided two-sample t-test with a significance level of 0.025 (per the Bonferroni adjustment for multiple comparisons) and an assumption of a standard deviation of 25 mm, a sample size of 40 subjects versus 20 subjects has a statistical power of 80% to detect a mean difference of 21.5 mm, a statistical power of 70% to detect a mean difference 19.5 mm, and a statistical power of 60% to detect a mean difference of 17.5 mm. Therefore, the sample size for Protocol VMDN-002 is determined to be 40 subjects in the VM202 16 mg group, 40 subjects in the VM202 32 mg group, and 20 subjects in the placebo group.

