5. GENERAL ANALYSIS CONSIDERATIONS

The statistical analyses will be reported using summary tables, figures, and data listings. Continuous variables will be summarized with means, standard deviations, medians, minimums, and maximums for each treatment arm. Categorical variables will be summarized by counts and by percentage of subjects in corresponding categories.

All analyses and tabulations will be performed using SAS[®] Version 9.2 or higher on a PC platform.

It should be noted that this Phase II study is for planning the future Phase III studies, therefore the p-values of the statistical tests should be used descriptively with clinically interpretation.

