5.2. Statistical Methods

Although the detectable effect size for the mean pain score reduction is calculated by the two-sided t-test with a significance level of 0.025 per Bonferroni adjustment, the Analysis of Variance (ANOVA) will be performed to detect any difference in the 6-month mean pain score reduction (as measured using the Daily Pain and Sleep Interference Diary) among the three study groups first and, if there is a significant findings based on ANOVA,

the Dunnett's test for the multiple comparisons will be used to compare each of the two VM202 groups and the placebo group in the 6-month mean pain score. Therefore, two-sided p-values <0.05 will be considered statistically significant, unless otherwise stated. As described previously, regardless of the statistical significance, the p-values of the statistical tests should be used descriptively with clinically meaningful interpretation.

Separate statistical tests will be performed at each time point for key endpoints of interest such as Visual Analogue Scale for Pain, Brief Pain Inventory for Diabetic Peripheral Neuropathy, Michigan Neuropathy Screening Instrument, Patients' Global Impression Change, and the [REDACTED] No adjustment for multiplicity will be performed.

In general, an overall test to determine if there is a statistically significant difference among the three treatment arms will be conducted first. Further comparisons will be made to determine if either the low or high dose groups are statistically significantly different from the placebo group.

For continuous variables, a one-way analysis of variance (ANOVA) with treatment group (high dose, low dose, and placebo) as a factor will be used to determine if there is a significant difference among the groups. The low and high dose groups will each be compared against the placebo group using Dunnett's test. The mean difference between the VM202 groups versus placebo along with 95% confidence intervals for the mean difference will also be presented.

For categorical variables, Fisher's exact test will be used to determine if there is a significant difference among the three treatment groups. Separate Fisher's exact tests will be used to compare the low and high dose groups to the placebo group.

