11. EFFICACY ANALYSES

The primary efficacy analysis will be based on the Efficacy Analysis Group. Additional efficacy analyses will be performed on the ITT Group.

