11.4. Multiplicity Adjustments

There will be no adjustments for multiple comparisons or interim analyses.

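### The normal-approximation interval for the responder difference falls a little short of 95% coverage at 40 v 20 and can contradict the SAP's own Fisher test

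*SAP*

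**What the plan says.** SAP 11.2 defines a responder as a subject with at least a 50% fall in average diary pain score from baseline to 6 months. It specifies three things for this outcome:

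- For each arm: "the corresponding 95% confidence intervals based on the binomial distribution will be calculated for each study group".
- For each active-placebo contrast: "The comparison between the placebo group and each of the two VM202 group will also be performed by Fisher's exact test".
- For the difference in that same contrast, a 95% interval that "will be derived by the two-sample normal distribution".

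The variance form (pooled or unpooled) and the use of a continuity correction are not stated. Nor does the SAP say which result prevails if the interval and the test disagree.

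SAP 4 plans "40 subjects in the VM202 16 mg group, 40 subjects in the VM202 32 mg group, and 20 subjects in the placebo group". SAP 11 adds: "The primary efficacy analysis will be based on the Efficacy Analysis Group". SAP 6 limits that group to subjects correctly dosed at both injection visits, with a 6-month assessment and no major deviation, so the placebo arm can fall below 20. SAP 5.2 sets the threshold: "two-sided p-values <0.05 will be considered statistically significant, unless otherwise stated". SAP 5 qualifies it: "the p-values of the statistical tests should be used descriptively with clinically interpretation". SAP 11.4 states: "There will be no adjustments for multiple comparisons or interim analyses".

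**The concern.** Within one section the test is exact and the per-arm intervals are binomial, yet the contrast that readers will quote gets a large-sample interval with about 20 subjects in one arm. Two things follow. The interval labelled 95% may cover less often than that. It may also exclude zero next to a Fisher p-value above 0.05 for the same comparison, with no rule for reading the pair. SAP 4 says the trial was sized to estimate effects and variability for a pivotal study, so the interval is the more useful output for planning, and an over-optimistic lower limit would carry forward.

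**Working it through.** **Inputs.** Arm sizes 40 and 20 are from SAP 4. The documents give no responder rates, so I assume 10-30% on placebo and 10-60% on active, in 5-point steps (5 × 11 = 55 rate pairs). The documents give no exclusion rate either; 32 v 16 assumes a 20% loss in each arm (0.8 × 40 = 32, 0.8 × 20 = 16). The variance is read as unpooled without continuity correction.

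**The plan's own figures.** The SAP gives no coverage or power for this outcome. The only computed figures at these arm sizes are those in SAP 4 for the two-sample t-test (alpha 0.025, SD 25 mm). Noncentral t with 58 df gives 79.7%, 70.7% and 60.2% power at 21.5, 19.5 and 17.5 mm, against the stated 80%, 70% and 60%. They reproduce.

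**Formulas.** With p1 = x/n1 (active), p2 = y/n2 (placebo) and d = p1 − p2:

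- Simple interval: d ± 1.96 × √[p1(1−p1)/n1 + p2(1−p2)/n2].
- Newcombe interval, with Wilson limits (l, u) for each arm: lower d − √[(p1−l1)² + (u2−p2)²], upper d + √[(u1−p1)² + (p2−l2)²].
- Coverage: the sum, over all x and y, of the two binomial probabilities for outcomes whose interval contains the true difference. At 40 v 20 there are 41 × 21 = 861 outcomes.

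**Example 1: 6/40 v 0/20.** d = 0.15. SE = √(0.15 × 0.85/40 + 0) = 0.0565; the placebo arm contributes nothing. The simple interval is 15.0 ± 11.1, or 3.9 to 26.1 points. Fisher p = 0.165. Newcombe gives −3.0 to 29.1.

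**Example 2: 16/40 v 3/20.** d = 0.25. SE = √(0.24/40 + 0.1275/20) = 0.111. The simple interval is 3.2 to 46.8 points (width 43.6). Fisher p = 0.077. Newcombe gives −0.1 to 43.2 (width 43.3). Newcombe is slightly narrower here; what differs is where the interval sits.

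**Coverage over the 55 rate pairs**

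| Arms | Simple | Newcombe |
|---|---|---|
| 40 v 20 | 91.6-94.3% (mean 93.4%) | 94.6-97.2% |
| 32 v 16 | 90.6-94.4% | 94.4-97.7% |

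The simple interval is below 95% at all 55 pairs for both sizes. With equal true rates of 10% at 40 v 20 it excludes zero in 8.4% of trials, against 2.8% for Newcombe. At equal rates of 20% the figures are 6.7% and 4.5%, with Fisher rejecting in 3.5%.

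**Conflict with Fisher at 40 v 20.** The simple interval excludes zero with Fisher p ≥ 0.05 in 42 of 861 outcomes, 21 of them favouring active. Newcombe does so in 22.

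| True placebo/active | P(conflict), simple | P(conflict), Newcombe |
|---|---|---|
| 10%/30% | 19% | 3% |
| 20%/40% | 14% | 4% |
| 20%/50% | 13% | 7% |

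**Width.** Newcombe is the narrower interval in 559 of 861 outcomes. Expected widths, simple v Newcombe, are 37.6 v 39.9 points at 10%/30%, 45.2 v 44.4 at 20%/40% and 49.6 v 47.1 at 30%/50%.

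**The case against.** The strongest reply is that the shortfall is small, rests on a reading the SAP does not spell out, and concerns a supportive outcome with descriptive p-values. Most of that stands.

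- *Reading.* Over true rates of 5-70% in each arm, pooled variance gives mean coverage of 95.3% and a continuity-corrected interval 96.7%. So the documents do not support saying flatly that the stated 95% limits are wrong. Conflicts with Fisher remain on either reading (28 and 12 of 861), and the ambiguity is itself a reason to name the method.
- *Width.* A reader might infer that the interval is simply too narrow. The widths above do not bear that out, except when placebo rates are low.
- *Fisher's conservatism.* Part of the disagreement comes from the test. Newcombe also excludes zero at 14/40 v 2/20 (p = 0.062) and 19/40 v 4/20 (p = 0.051). But the simple interval's 8.4% and 6.7% exclusion rates under equal true rates exceed 5% without any reference to Fisher.
- *Extreme figures.* Coverage can fall much further at very low rates: 86.5% at placebo 10% and active 5%. That has active doing worse than placebo and should not be used to size the problem. At 5%/5% coverage is 94.8%.
- *Consequence.* A reader might infer that a trial conclusion is at risk. No decision rule uses this interval, and SAP Appendix A lists no responder table, so it is only presumed that the interval and p-value would be printed together.

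The descriptive status of p-values does not remove the point, because it shifts weight onto the interval.

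**Conclusion.** The point holds as a minor one. On the ordinary reading and the assumed rates, the interval falls about 1 to 3 points short of nominal at 40 v 20 (95 − 94.3 = 0.7 to 95 − 91.6 = 3.4; mean 95 − 93.4 = 1.6), and slightly more at the assumed 32 v 16. When the true benefit is 20-30 points, the chance that it contradicts the SAP's own test is roughly one in eight to one in five. The responder rates, the 32 v 16 set and the unpooled, uncorrected form are assumptions. The primary analysis, the sample size and the safety conclusions are untouched.

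**What to change.** In SAP 11.2, before unblinding, replace the normal-approximation interval for each VM202 group minus placebo with the Newcombe interval built from Wilson score limits, or with an exact unconditional interval. Add that Fisher's test governs if the interval and the test disagree. That rule is needed because neither choice guarantees agreement; only inverting the exact test actually used would do so.

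The cost is one or two SAP sentences and a small programming change. SAP 5 allows SAS 9.2 or higher, so confirm that the release in use offers the chosen interval; if not, the Newcombe formula above is short to code. No new data and no design change are needed. Intervals become somewhat wider at low responder rates and similar or narrower elsewhere.

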11.3. Other Efficacy Variables

The analyses for the other efficacy variables will be performed based on the Efficacy Analysis Group unless specified otherwise. No imputation for the missing data will be performed for these efficacy endpoints. These efficacy endpoints include:

11.3.1. VISUAL ANALOGUE SCALE FOR PAIN (VAS)

Subjects will be asked to assess the level of pain they feel by placing a perpendicular line on a scale of 0 (No Pain) to 100 mm (Very Severe Pain) at Day-0, Day-30, Day-60, Day-90, 6-Month, and 9-Month Visits at the clinic. This is a separate analysis from the 7-Day Daily Pain and Sleep Interference Diary. The subject's Visual Analogue Scale (VAS) score will be determined by where the subject places the perpendicular line. The average of the VAS measured by two readers will be calculated for each subject at each visit. The VAS measurements and change from baseline (average of VAS at screening and Day 0, or if data are missing from either, the value recorded at either visit will be summarized at each required visit by treatment arm using method for continuous variables.

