POPULATION	Subjects aged ≥ 18 years to ≤ 75 years diagnosed with painful diabetic neuropathy in both lower extremities.
STUDY DESIGN	A phase II, double-blind, randomized, placebo-controlled, multicenter, 9-month study designed to assess the safety and efficacy of bilateral intramuscular (IM) injection of VM202 in the calf of subjects with painful diabetic peripheral neuropathy (DPN). One-hundred (100) subjects will be randomized in a 2:2:1 ratio to one of three treatment groups: Low Dose: 16 mg VM202 - 40 subjects High Dose: 32 mg VM202 - 40 subjects Control – Placebo (normal saline) - 20 subjects Up to twenty (20) sites will participate in the study. Safety will be monitored throughout the study and assessed by an independent Data Safety Monitoring Board (DSMB).
STUDY OBJECTIVES	
• To evaluate the safety of IM administration of VM202 in subjects with painful DPN in lower extremities.• To evaluate the potential bioactivity of IM administration of VM202 in subjects with painful DPN, when compared with placebo, on pain.
INCLUSION CRITERIA	
1. Age ≥ 18 years to ≤ 75 years;2. Documented history of Type I or II diabetes with current treatment control (glycosylated hemoglobin A_{1c} of $\leq 10.0\%$ at

Screening) and currently on oral medication and / or insulin

3. Diagnosis of painful diabetic peripheral neuropathy in both lower extremities;
4. Lower extremity pain for at least 6 months
5. Visual analog scale (VAS) score of ≥ 40 mm at Initial Screening (0 mm = no pain – 100 mm very severe pain);
6. Symptoms from the Brief Pain Neuropathy Screening (BPNS) is ≤ 5 point difference between legs at Initial Screening;
7. The average daily pain intensity score of the Daily Pain and Sleep Interference Diary completed after medication wash-out is ≥ 4 with a standard deviation ≤ 2 ;
8. The physical examination component of the Michigan Neuropathy Screening Instrument Score (MNSI) is ≥ 3 at Screening;
9. Stable treatment of diabetes for at least 3 months with no anticipated changes in medication regimen, and no new symptoms associated with diabetes; and
10. If female of childbearing potential, negative urine pregnancy test at screening and using acceptable method of birth control during the study.

EXCLUSION CRITERIA

1. Peripheral neuropathy caused by condition other than diabetes;
2. Other pain more severe than neuropathic pain that would prevent assessment of DPN;

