3.4.3. SCREENING (DAY -60 TO DAY 0)

Prior to full screening, subjects will give informed consent and then be initially screened using the VAS, the Symptoms portion of the BPNS and the MNSI. Only subjects with a VAS score of $\geq 40 \text{ mm}$, a ≤ 5 point difference in symptom of BPNS between legs and MNSI score of ≥ 3 will be allowed to proceed with the full screening procedures.

If the VAS, BPNS and MNSI criteria are met, the rest of screening will proceed. If applicable, the subject will be washed out of prohibited medications. During medication wash-out and prior to randomization, subject eligibility will be assessed as follows:

- Evaluation of Eligibility Criteria
- Complete Medical History
- Concomitant Medications
- Vital Signs, including height
- Complete Physical Exam,
- EKG
- HbA1c
- Serum chemistry and hematology
- Urinalysis
- Urine pregnancy test (for women of childbearing potential only)
- Cancer screening should be conducted per the current American Cancer Society Guidelines for the Early Detection of Cancer. Testing should also include: pap smear and mammogram if not performed within past 12 months (females only); chest X-ray or chest CT scan (if the subject has a previous history of tobacco use, a CT scan will be performed instead of X-ray) within 3 months prior to study entry; PSA within past 3 months (males only);[†] for subjects ≥ 50 years old, colonoscopy within past 10 years; for subjects with family history of colon cancer in any first degree relative, colonoscopy within past 12 months.
- Viral screening – HIV, Anti-Human T-Cell Lymphotropic Virus (HTLV), Positive Hepatitis B or C as determined by Hepatitis B core antibody (HBcAb), antibody to Hepatitis B antigen (IgG and IgM; HBsAb), Hepatitis B surface antigen (HBsAg) and Hepatitis C antibodies (Anti-HCV), at Screening
- Retinal Fundoscopy – in cases where fundoscopy alone is deemed insufficient to rule out exclusionary conditions (see exclusion criterion # 12), fluorescein angiography may be conducted

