Appendix 3. Medications Excluded from Use During the Study

WASHOUT TABLE FOR COX-2 INHIBITORS & STEROIDS

Drug	Example of Common Name(s)	Minimum Dose Allowed During Study	Washout Period
Cox-2 specific Inhibitors			
celecoxib	Celebrex	none	2 weeks
Non-steroidal Anti-inflammatory Drugs (NSAIDs: nonspecific inhibitors of both Cox-1 and Cox-2)			
acetylsalicylic acid	Aspirin Arthritis Foundation Safety Coated Aspirin, Bayer Aspirin, Bayer Children's Aspirin, Ecotrin	81 mg daily	2 weeks for doses over 81 mg daily
diclofenac	Voltaren Arthrotec, cambia, cataflam, flector, pennsaid, solaraze, zipsor	none	2 weeks
diflunisal	Dolobid	none	2 weeks
etodolac	Lodine	none	1 week
fenoprofen	Nalfon	none	1 week
flurbiprofen	Ansaid	none	1 week
ibuprofen	Motrin, Advil, caldorol, profen	none	1 week
idomethacin	Indocin	none	1 week
ketoprofen	Nexcede, Orudis	none	None for topical formulation, 1 week for all others
ketorolac	Sprix, acuvail, acular	none	1 week
mefenamic acid	Ponstel	none	1 week
meloxicam	Mobic	none	1 week
nabumetone	Relafen, Relifex and Gambaran	none	1 week
naproxen sodium	Aleve, Anaprox, Antalgin, Feminax Ultra, Flanax, Inza, Midol Extended Relief, Miranax, Naposin, Naprelan, Naprosigic, Naprosyn, Narocin, Proxen, Synflex, Xenobid	none	2 weeks
oxaprozin	Daypro	none	1 week
piroxicam	Feldene	none	1 week
sulindac	Clinoril	none	1 week
tolmetin	Tolectin	none	1 week
Corticosteroids (topical, injected, oral)	Prednisone, betamethasone, dexamethasone, cortisone, triamcinolone	none†	1 week

Please note, some of these medications are provided in combination with other drugs in new formulations (e.g. AGGRENOX® (aspirin/extended-release dipyridamole); Excedrin (acetaminophen; aspirin; caffeine))

† inhaled steroids for the treatment of respiratory disorders are allowed

WASHOUT OF OPIOIDS

Since opioids may interfere with assessment of VM202 effect on pain, subjects must discontinue use of all opioid drugs fourteen days prior to the completion of the Daily Pain and Sleep Interference Diary at Screening.

Subject must agree to remain off of these medications until completion of the 9 month follow-up visit.

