Appendix 8. Visual Analog Scale

The VAS will be completed by the subject. The subject should be asked: “**How do you currently rate your pain in your legs (below the knee – this includes pain in your feet)?**”

The subject should be instructed to indicate his or her current level of pain in their legs by placing a single vertical line perpendicular to the horizontal line of the scale ensuring that the two lines intersect. Additionally, the subject should be instructed to not use a check mark, “x” or circle that would intersect the horizontal line of the scale multiple times. Ensure the subject understands that the mark must be only one line that is perpendicular to and intersects the scale line. The subject should complete the VAS with a fine or medium point pen; felt tip pens and pencils should not be used.

No pain | _____ | Very severe pain

The VAS should be checked for accuracy and completeness immediately after it is completed by the subject. If the subject’s mark does not intersect the line or intersects the line more than once, reinstruct the subject to modify his or her mark so it meets the appropriate criteria. Any corrections should be accompanied by the subject’s initial and date. For Day 0 , all corrections MUST be completed prior to injections; do NOT have the subject correct the scale after injections. Instead, use the data collected prior to dosing.

The VAS score (0 to 100mm) will be calculated by measuring the distance from the left end of the line (“No Pain”) along the scale to the mark made by the subject. If the mark made by the subject intersects the horizontal line of the scale multiple times and was not corrected, measure to the middle point between the two marks. If the mark made by the subject does not intersect the line of the scale and was not corrected, project the location of the mark vertically to a point on the line of the scale for the measurement.

[figure not shown]

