Adverse Event	An adverse event (AE) is the development of an untoward medical occurrence or the deterioration of a pre-existing medical condition following or during exposure to an investigational product, whether or not it is considered causally related to the product.
Baseline	The last non-missing value prior to first dose of study drug.
Serious AE	Any untoward medical occurrence which results in death; is a life-threatening experience; requires hospitalization (admission to hospital with a stay > 24 hours) or prolongation of an existing hospitalization which is not specifically required by the protocol or is elective; Results in permanent impairment of a body function or permanent damage to a body structure; or requires medical or surgical intervention to preclude permanent impairment of a body function or permanent damage to a body structure

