9. BASELINE VALUES

Unless specified otherwise, the baseline value for each variable is the value recorded at the last visit on or before start of dosing.

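### The VAS baseline averages in the entry-selected, pre-wash-out screening value, so within-arm VAS change carries an avoidable shift of unknown sign, roughly -3 to +2 mm under assumed inputs

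*SAP*

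**What the plan says.** SAP 11.3.1 defines VAS "change from baseline (average of VAS at screening and Day 0, or if data are missing from either, the value recorded at either visit". The SAP's definitions table gives baseline as "The last non-missing value prior to first dose of study drug", which for VAS is the Day 0 reading. SAP section 9 says much the same ("the baseline value for each variable is the value recorded at the last visit on or before start of dosing"), but its opening clause allows exceptions.

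The protocol sets the order of events. Entry requires a "Visual analog scale (VAS) score of ≥ 40 mm at Initial Screening". Section 3.4.3 takes that VAS straight after consent and continues: "If the VAS, BPNS and MNSI criteria are met, the rest of screening will proceed. If applicable, the subject will be washed out". A second VAS is recorded on Day 0 before injection (Protocol 3.2 and 3.4.8.1). Appendix 3 explains the opioid wash-out: "Since opioids may interfere with assessment of VM202 effect on pain". Section 3.4.4.1 gives a different reason for COX inhibitors, namely interference with the bioactivity of VM202.

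VAS is a secondary endpoint (Protocol 6.3.2). SAP 5.2 compares the arms by one-way ANOVA and Dunnett's test.

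**The concern.** Two features make the screening VAS a poor half of a baseline.

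- **Selection.** Subjects enter because this reading was at least 40 mm. Its chance error is on average upward among those enrolled, and later readings fall back. Half of that excess enters every subject's averaged baseline and appears as improvement.
- **Wash-out.** In a subject who had to stop an opioid, the screening reading may be lower than the off-drug readings that follow. Half of that difference enters the baseline and appears as worsening. The diary baseline must follow wash-out (Protocol 3.4.3 and 4.2.8); the averaged VAS baseline has no such protection. If the Day 0 value is missing, the whole baseline is the selected, pre-wash-out value.

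What is at stake is the within-arm VAS change. SAP section 4 quotes this quantity from Phase I (an overall reduction of about 23 mm) and says the present trial is meant to estimate effect sizes and variability for a pivotal study. A shift of unknown sign in that estimate can be avoided, because a Day 0 reading is already collected.

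**Working it through.** **Plan's own figure.** SAP section 4 uses 40 v 20 subjects, SD 25 mm and two-sided alpha 0.025. SE = 25 × sqrt(1/40 + 1/20) = 6.85 mm. The noncentral t distribution with 58 df gives power of 79.7%, 70.7% and 60.2% at 21.5, 19.5 and 17.5 mm, against the stated 80%, 70% and 60%. The figures reproduce. They are framed around the diary and do not depend on the VAS baseline rule.

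**Inputs the documents do not give.** These are the mean (mu) and SD of screening VAS, the correlation rho between readings, the share f of subjects washed out, and the rise w in pain after wash-out. All are assumed below.

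**1. Selection.** With a = (40 - mu)/SD, the excess in the screening VAS is (1 - rho) × SD × phi(a)/[1 - Phi(a)], and half of it enters the average.
- Example: mu 60, SD 20, rho 0.6. Then a = -1 and phi/(1 - Phi) = 0.242/0.841 = 0.288. The excess is 0.4 × 20 × 0.288 = 2.3 mm, and half is 1.15 mm.
- Over mu 50 to 70, SD 15 to 25 and rho 0.5 to 0.8, the half-excess is 0.1 to 3.5 mm of false improvement.

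**2. Wash-out.** The baseline falls by f × w/2. For f 5 to 50% and w 5 to 20 mm this is 0.1 to 5.0 mm of false worsening.

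**3. Net effect, no true change.** The two parts do not simply subtract. A subject whose screening VAS was lowered by a drug is less likely to pass 40 mm, and is more strongly selected if he or she does. Two simulations were used.
- Equal correlations (mu 50 to 60, SD 20 to 25, rho 0.5 to 0.6, f 0 to 50% before the cut, w up to 20 mm): about -3.0 to +1.8 mm.
- Off-drug mean 50 to 65 mm, between-subject SD 18, within-visit SD 15, later drift SD 12, f 0 to 50%, w 10 to 20 mm: -2.6 to +2.0 mm. Washed-out subjects show about +1.2 to +6.8 mm, the others about -1.2 to -2.7 mm.

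Change from Day 0 is about zero in both when the VAS cut is the only selection.

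**4. Arm contrast.** With a true difference of -15 mm, both baselines return -15.0 to -15.2 mm. The shift is common to the randomised arms.

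**5. Day 0 under the diary cut.** Entry also requires a mean diary score of at least 4 shortly before dosing. Suppose that 30 to 60% of the Day 0 within-visit variance is shared with the diary week, that the diary scale is multiplied by 10 to match mm, and that nobody is washed out. Change from Day 0 then shows about -0.4 to -2.3 mm, and change from the average about -1.2 to -3.0 mm.

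**6. Precision** (second model in step 3, before truncation).
- Change from Day 0: sqrt(225 + 225 + 144) = 24.4 mm.
- Change from the average: sqrt(225 + 112.5 + 144) = 21.9 mm (21.7 to 22.0 simulated).
- Both values as covariates: sqrt(693 - 324²/436.5) = 21.3 mm (21.3 to 21.5 simulated). Here 693 = 324 + 144 + 225 is the follow-up variance and 436.5 = 324 + 112.5 is the variance of the mean of the two baselines.

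**The case against.** The strongest defence is that averaging two pre-dose readings is a legitimate choice for precision, prespecified under the exception that SAP section 9 allows. That stands in part. The definitions table carries no such exception, but section 9 does, so this is a wording conflict to reconcile and not a breach. The precision gain is real. Under equal correlations, unadjusted change from Day 0 has an SD sqrt(2/1.5) = 1.155 times larger. If 25 mm were the SD with the averaged baseline, Day 0 alone would give 28.9 mm, and power at 21.5 mm would fall from 80% to 66%. The arm comparisons should therefore not simply move to unadjusted change from Day 0.

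It is also fair to say that Day 0 is not perfectly clean (step 5), and that subjects may stop existing neuropathy drugs during follow-up (Protocol 3.4.4.2), which confounds within-arm change under any baseline.

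The documents do not support four stronger readings that a reader might reach:
- **Half of everyone's baseline is taken on drugs that distort pain.** Wash-out applies only where needed, other neuropathy drugs are not washed out, and the pain-assessment reason is stated for opioids only. The synopsis also lists VAS among screening assessments and lets those other than the diary be scheduled during wash-out, although Protocol 3.2 and 3.4.3 put the VAS first.
- **The dose-placebo contrast is biased.** Randomisation prevents this in expectation. Chance imbalance in the washed-out share is ordinary sampling error.
- **The within-arm bias has a known direction.** The two mechanisms oppose each other.
- **The two-reader average in SAP 11.3.1 ("The average of the VAS measured by two readers will be calculated for each subject at each visit") is an error.** Protocol 4.2.7 and Appendix 8 ("The VAS score (0 to 100mm) will be calculated by measuring the distance from the left end of the line") say how the mark is measured, not by how many people. No harm is shown.

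**Conclusion.** The point holds for within-arm VAS change only. Half of the baseline is an entry-selected reading taken before any wash-out, although a pre-injection Day 0 reading exists and fits the SAP's own definition. The net false change is roughly -3 to +2 mm, of unknown sign and possibly near zero; at most it is about an eighth of the 25 mm SD (3/25 = 0.12). Every input behind that range is assumed. Selection affects all subjects whatever their drug use; the opposite shift affects only those washed out. The planned VAS comparisons with placebo remain unbiased in expectation. The diary primary endpoint has its own baseline sentence in SAP 11.1 and is not affected by this rule. The issue is minor, but the remedy loses no precision in the arm comparisons.

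**What to change.** In SAP 11.3.1:

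1. Report within-arm VAS change from the Day 0 pre-injection value, in line with the SAP definitions table. Note that it may keep some selection effect from the diary entry criterion.
2. For the dose-placebo VAS comparisons, replace the one-way ANOVA on change with a model that has treatment, Day 0 VAS and screening VAS, and keep the Dunnett comparisons.

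Both readings are already collected, so the cost is SAP text and programming. There are two downsides. Unadjusted change from Day 0 has an SD about 11 to 12% larger than change from the average (24.4/22.0 = 1.11; 24.4/21.7 = 1.12). The comparison model also becomes ANCOVA, a change of method that SAP 5.2 must reflect for this endpoint. In return, its residual SD matches or slightly improves on that of the averaged baseline.
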